# **5.1.1.3.** Treatment-emergent Treatment-Related Adverse Events (TRAEs)

A TRAE is any TEAE that is related to any study treatment.

# 5.1.1.4. Adverse Event of Clinical Interest (AECI)

Any AE (serious or non-serious) that is of scientific and medical concern specific to the study treatment, for which ongoing monitoring and rapid communication by the Investigator to the Sponsor is appropriate.

# **5.1.2.** Analysis Methods

The primary focus of AE reporting will be on TEAEs.

If an AE date/time of onset (occurrence or worsening) is incomplete, an imputation algorithm will be used to determine the AE as treatment-emergent. The algorithm for imputing date/time of onset will be conservative and will classify an AE as treatment-emergent unless there is definitive information to determine it is not treatment emergent. Details on classification of AEs with missing or partial onset dates are provided in Section 2.2.2.

AE summaries will include number (n) and percentage (%) of patients who have experienced an AE. The denominator for computation of percentages is the number of patients in the corresponding treatment arm. Multiple occurrences of the same event in the same patient will be counted only once in the tables.

Unless otherwise specified, sorting order will follow the alphabetic order in SOC, and further by decreasing frequency of PTs within each SOC. When more than one PT has same number of events, the order of presentation will be alphabetical in PTs.

The summary of AEs by causality will generally include the following categories of causality.

- Related to either KPT-9274 or niacin or nivolumab
- Related to KPT-9274 only
- Related to niacin only
- Related to nivolumab only
- Not related to KPT-9274 or niacin or nivolumab

# **5.1.3.** Analysis of TEAE

An TEAE overview summary table will be provided, which will include the number of patients with at least one of the adverse events:

- TEAEs
- Grade 3/4 TEAEs
- Serious TEAEs
- TEAEs leading to dose modifications of study treatment
- TEAEs leading to dose reduction of study treatment
- TEAEs leading to dose interruption of study treatment
- TEAEs leading to study treatment discontinuation
- TEAEs leading to death
- TRAE
- Serious TRAEs
- TRAEs leading to dose modifications of study treatment
- TRAEs leading to dose reduction of study treatment
- TRAEs leading to dose interruption of study treatment
- TRAEs leading to study treatment discontinuation
- TRAEs leading to death

TEAEs will be summarized by primary SOC and PT and will include the following categories:

- All TEAEs
- All TEAEs, by causality
- All TEAEs, by maximum grade
- Grade 3 or higher TEAEs
- Grade 3 or higher TEAEs, by causality
- TEAEs leading to dose modifications of study treatment

• TEAEs leading to study treatment discontinuation

The most commonly reported (at least 10% of all patients) TEAEs will be presented by PT only and will include the following categories:

- The most commonly reported TEAEs
- The most commonly reported TEAEs related to study treatment

# 5.1.4. Analysis of SAE

Treatment-emergent SAEs will be summarized by primary SOC and PT and will include the following categories:

- All treatment-emergent SAEs
- All treatment-emergent SAEs, by causality
- Treatment-emergent SAEs leading to dose modifications of study treatment
- Treatment-emergent SAEs leading to study treatment discontinuation

All SAE will be provided in a data listing.

# 5.1.5. Analysis of DLTs

DLT will be summarized in the dose escalation population. A data listing will be provided for DLTs.

# 5.1.6. Analysis of AECI

Standard MedDRA Query (SMQ), Customized MedDRA Query (CMQ) will be utilized for AECI analysis. Analyses of treatment-emergent AECI will be performed separately for each pre-specified AECI category. Overview summary of all AECI will be summarized similarly as in Section 5.1.3.

The following AECI will be summarized by PT:

- All TEAEs
- Serious TEAEs

The list of AECI categories are provided in Table 5-1. The search strategy of preferred terms for each category will be provided in a separate document.

Table 5-1 AECI Categories

Group Category	AECI Category	
Hematologic events	Anaemia	
	Neutropenia	
	Thrombocytopenia	
	Decreased Appetite	

Constitutional events	Weight Decreased	
Eye disorders events	Blurred Vision	
	Cataract	
Gastrointestinal events	Nausea	
	Vomiting	
Infection	Pneumonia	
	Opportunistic Infection	
	Sepsis	
Metabolism and nutrition disorders	Hyponatremia	
Nervous system disorders	Neurological Toxicity	
Others	Hepatobiliary Disorders	
	Cardiac Toxicity	

# **5.2. DEATH**

The following summaries on death events will be provided:

- An overview of all death events and primary cause of death
- TEAEs leading to death (death as an outcome on the AE report page as reported by the Investigator), by primary SOC and PT
- TEAEs leading to death and are related to study treatment, by primary SOC and PT
- TEAEs leading to death and are related to KPT-9274 only, by primary SOC and PT
- TEAEs leading to death and are related to niacin only, by primary SOC and PT
- TEAEs leading to death and are related to nivolumab only, by primary SOC and PT
- Listing of all TEAEs leading to death
- Listing of all death events

# **5.3.** LABORATORY SAFETY VARIABLES

#### 5.3.1. Definitions

Clinical laboratory data of interest consists of blood analysis, including hematology and serum chemistry and coagulation. Clinical laboratory values in conventional units will be converted using the international system of units (SI).

The laboratory parameters will be classified as follows:

- Hematology test will be performed at screening visit, on day 1 of every cycle, and at the EoT visit.
- Complete Serum Chemistry panel will be measured at Screening Visit on day 1 of every cycle and at the EoT visit.
- Coagulation test will be performed at screening visit and at the EoT visit.

Table 5-2 presents the clinical laboratory tests that will be analyzed.

**Table 5-2 Clinical Laboratory Tests** 

Complete Blood Count with Differential (Blood sample: whole blood; ethylenediaminetetraacetic acid) tests including)				
Hemoglobin	Hematocrit	Mean corpuscular volume	Mean corpuscular hemoglobin	Mean corpuscular hemoglobin concentration
WBC count	WBC differential  (Parts A and B Only)	RBC count	Lymphocytes	Monocytes
Neutrophils	Eosinophils	Basophils	Platelets	Reticulocyte count
Complete Serum Cl	nemistry (Blood sample	e: serum)		
Sodium	Potassium	Chloride	Bicarbonate	Blood urea nitrogen
Creatinine	Glucose	Calcium	Phosphate	Magnesium
ALT	AST	Alkaline Phosphatase	Total bilirubin 	Lactate dehydrogenase
Total protein	Albumin	Amylase	Lipase	Creatinine kinase
Urate	Thyroid-stimulating hormone			
Coagulation				
Prothrombin time (Parts A and B Only)	International normalization ratio (Parts A and B Only)	Activated thromboplastin time (Parts A and B Only)		

Abbreviations: ALT = alanine aminotransferase; AST = aspartate aminotransferase; RBC = red blood cell; ULN: upper limit of normal; WBC = white blood cell.

# **5.3.2.** Analysis of Laboratory Variables

Whenever applicable, severity of selected clinical laboratory measures will be determined based on the CTCAE criteria. The worst toxicity grade in hematology and chemistry will be summarized by toxicity grade. Shift tables that present changes from baseline to worst on-study

 WBC differential may be automated or manual as per institutional standards. Blasts should be included.

 If the total bilirubin concentration is increased > 1.5 × ULN, total bilirubin should be differentiated into the direct and indirect reacting bilirubin.> 1.5 ULN, total bilirubin should be differentiated into the direct and indirect reacting bilirubin.

relative to CTCAE classification ranges will be presented. These shift tables will include results from unscheduled visits.

For several key laboratory parameters, box plots on measurements over time as well as by-patient plots for patient-level measurements over time may be presented.

A listing of cases where ALT or AST > 3x upper limit of normal (ULN) with simultaneous total bilirubin > 2x ULN will be presented.

Thresholds/Range analyses for selected laboratory parameters will be conducted. The number and percentage of patients classified into each category based on worst values will be presented.

# 5.4. VITAL SIGNS, AND ECOG VARIABLES

The physical examination will be performed according to the standards at each institution.

A full physical examination including vital signs will be performed at Screening Visit and EOT visit.

Symptom-directed physical examination, vital signs, and ECOG will be performed as per the schedule of assessments (SOA).

The actual value and change from baseline to each on-study evaluation will be summarized for vital signs including pulse, temperature, systolic blood pressure, diastolic blood pressure, BSA and weight. Shift tables that present changes from baseline to highest on-study and lowest on-study for systolic blood pressure and diastolic blood pressure will be presented. Shift tables that present changes from baseline to worst on-study and last on-study ECOG performance status values will also be produced.

Abnormal vital signs results will be summarized in the threshold/range analyses.

All vital sign measurements, physical examination results and ECOG performance status scores may also be provided in data listings.

# 5.5. ELECTROCARDIOGRAM (ECG)

Standard 12-lead electrocardiogram (ECG) will be performed at screening (day -30 to day -1), C1D1 (pre-dose and 4 hours post-dose), C1D26 (pre-dose and 4 hours post-dose), C2D1, day 1 of odd numbered cycles starting at cycle 3, at the EoT visit, and as clinically indicated at the discretion of the Investigator. Electrocardiograms may also be performed as clinically indicated during the study. Patients must rest for at least 5 minutes prior to the ECG recording. Patients must rest for at least 5 minutes prior to any ECG recording. The Investigator will interpret the ECG using 1 of the following categories: normal, abnormal but not clinically significant, or abnormal and clinically significant. The following will be assessed: heart rate, PR interval, QRS interval, and QT corrected using Fridericia's formula (Fridericia, 1920).

Changes from baseline to highest on-study post baseline measurement for PR interval, QRS interval, and QT corrected will be summarized using shift tables. For heart rate, changes from baseline to lowest and highest on-study post baseline measurement will be presented.

Abnormal ECG results will be summarized in the threshold/range analyses.

Electrocardiogram data for each patient may also be provided in a data listing.

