- 12-Lead ECG to be completed at Screening (Day -30 to Day -1), C1D1 (pre-dose and 4 hours post-dose), C1D26 (pre-dose and 4 hours post-dose), C2D1, Day 1 of odd numbered cycles starting at Cycle 3, at the EoT visit, and as clinically indicated at the discretion of the Investigator. See Section 9.6.1.3 for a detailed description of electrocardiography.
- Echocardiogram or MUGA scan at Screening (Day -30 to Day -1), EoT and as clinically indicated at the discretion of the Investigator during the study. See Section 7.5.1.3 for a detailed description of echocardiography.
- A full ophthalmic examination at Screening (Day -30 to Day -1) and EoT will include, prior to dilation, best corrected visual acuity, slit lamp examination including tonometry, following dilation; fundoscopy and slit lamp to document lens clarity. See Section 7.5.1.4 for a detailed description of ophthalmic examination.
- The following procedures must be performed at Screening (Day -30 to Day -1) and pre-dose on C1D1 (and as shown in Table 1, Table 2, and Table 3 during the study): ECOG performance assessment, echocardiogram or MUGA scan (Screening only), 12-lead ECG, and ophthalmic exam (Screening only). The following procedures must be performed at Screening (Day -14 to Day -1) and pre-dose on C1D1 (and as shown in Table 1, Table 2, and Table 3 during the study): urinalysis, CBC with differential, TSH, complete serum chemistry, coagulations tests (Screening only), amylase, and lipase.
- TSH, amylase and lipase do not need to be repeated separately if included in serum chemistry.

10 For females of childbearing potential, negative serum hCG pregnancy test must be performed \leq 3 days of C1D1 and the EoT Visit. Repeat testing during the study as clinically appropriate. Test sensitivity for hCG must be \geq 25 mIU/mL.

11 Disease risk assessment: See Section 7.2.3 for additional details.

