Abbreviations: AE = adverse event; BSA = body surface area; CBC = complete blood count; CT = computed tomography; D = Day; ECG = electrocardiogram; ECOG = Eastern Cooperative Oncology Group; EORTC QLQ = European Organization for Research and Treatment of Cancer Quality of Life Questionnaire; EoT = End of Treatment; FACT-Lym = Functional Assessment of Cancer Therapy-Lymphoma; MRI = magnetic resonance imaging; PET = positron emission tomography; **CCI** [REDACTED]; PK = Pharmacokinetic; TSH = thyroid stimulating hormone

- 1 Prior to any study-specific measure.
- 2 Confirmation patients with melanoma who progressed on prior anti-PD-1 or anti-PD-L1 treatment.
- 3 A complete medical history will be obtained from each patient. Medical history will include baseline symptoms of the disease under study as well as a detailed history of prior procedures for the patient's melanoma and other prior cancer therapies (i.e., chemotherapy, hormonal therapy, immunotherapy, biotherapy, radiotherapy, and surgery), including start and end dates, best response, disease progression during or after therapy, as well as discontinuations due to intolerance, toxicity, or any other serious illness; Tumor Nodes Metastasis (TNM) staging will be collected on for patients. Smoking history will be recorded. A detailed history of disease-specific diagnostic and prognostic testing and test results (such as phenotypic and cytogenetic profiles) will also be collected.
- 4 Vital signs: blood pressure, pulse and body temperature; see Section 7.5.1.2 for a detailed description of vital sign assessments.
- 5 12-Lead ECG (in triplicate) to be completed at C1D1 (pre-dose and 4 hours post-dose), at the EoT visit, and as clinically indicated at the discretion of the Investigator. See Section 9.6.1.3 for a detailed description of electrocardiography.
- 6 Echocardiogram or MUGA scan at Screening (Day -30 to Day -1), and as clinically indicated at the discretion of the Investigator during the study. See Section 7.5.1.3 for a detailed description of echocardiography.

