7.5.1.3. Echocardiography and Electrocardiography

An echocardiogram or multiple gated acquisition (MUGA) scan to assess cardiac function and risk of cardiac dysfunction, including cardiomyopathy is required at Screening (Day -30 to Day -1) and at the EoT Visit. Additional echocardiogram or MUGA scans may be performed

throughout the study if clinically indicated at the discretion of the Investigator. The same procedure (either MUGA or echocardiogram) should be performed at screening/baseline and subsequent visits. Preferably the same cardiologist/radiologist should read and report the outcome to minimize variability in results. Copies of all transthoracic echocardiograms and/or MUGA scans performed on subjects who experience a greater than or equal to 20% decrease in left ventricular ejection fraction (LVEF) from baseline and whose cardiac ejection fraction is below the institution's lower limit of the normal range (LLN) will be required by Karyopharm for review.

A single standard 12-lead ECG will be performed for patients in Part A and B. Patients must rest for at least 5 minutes prior to the ECG recording. The Investigator will interpret the ECG using one of the following categories: normal, abnormal but not clinically significant, or abnormal and clinically significant. The date and time the ECG is performed and the following parameters will be recorded in the eCRF: heart rate, PR interval, QT interval, QRS interval, and QT corrected using Bazett's formula.

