# 2.6. BASELINE MEASUREMENT

For treatment period, the baseline value is defined as the latest value prior to the first dose of study treatment.

In the case an assessment performed on the same date as the first dose, but it is impossible to determine the evaluation time relative to the time of taking the first dose, the evaluation time will be assumed to be following the protocol-defined schedule.

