# 5. SAFETY

Safety analyses will use safety population. Each tumor type will be analyzed separately with the outputs presented by part and cohort and for all patients combined.

Safety and tolerability of KPT-9274 will be evaluated by means of DLTs (dose escalation cohorts only), AE reports, electrocardiograms and laboratory safety evaluations.

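### SAP 5.5 gives Part C the wrong ECG schedule, has no rule for its triplicates, and summarises PR, QRS and QTc by a maximum that grows with the number of recordings

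*SAP*

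**What the plan says.** **Summary statistic.** SAP 5.5: "Changes from baseline to highest on-study post baseline measurement for PR interval, QRS interval, and QT corrected will be summarized using shift tables". Heart rate is handled in the same way, for both lowest and highest values. Abnormal results also go into threshold/range categories, and a listing is optional. No other interval summary appears in that section.

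**Schedule in the SAP.** After screening and C1D1, SAP 5.5 continues with "C1D26 (pre-dose and 4 hours post-dose), C2D1, day 1 of odd numbered cycles starting at cycle 3, at the EoT visit". It names no part.

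**Schedule in the protocol.** Tables 1–3, footnote 5 (Parts A and B) carries the same list: "C1D26 (pre-dose and 4 hours post-dose), C2D1, Day 1 of odd numbered cycles starting at Cycle 3, at the EoT visit". Tables 5–7, footnote 5 (Part C) differs: "12-Lead ECG (in triplicate) to be completed at C1D1 (pre-dose and 4 hours post-dose), at the EoT visit, and as clinically indicated". Table 6, which covers Part C from Cycle 2 onward, has no ECG row. On replicates, protocol 7.5.1.3 says: "A single standard 12-lead ECG will be performed for patients in Part A and B".

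**Baseline.** SAP 2.6: "the baseline value is defined as the latest value prior to the first dose of study treatment". Neither document says how three tracings at one time point become one value.

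**Related rules.** The general rules in SAP 5 let unscheduled readings count toward worst values. SAP 2.7 defines analysis windows for laboratory tests and vital signs, but not for ECG. SAP 1.5 sets no limit on treatment duration.

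**The concern.** A maximum depends on how many readings it is taken over and on how noisy each one is. Both differ here for reasons unrelated to the drug. In Parts A/B the number of single recordings rises with time on treatment, so a cohort treated for longer shows higher maxima even if KPT-9274 has no effect on the ECG. In Part C there are always two scheduled post-baseline time points, but six tracings. The SAP does not say whether the analysis value is the mean of three tracings, one of them, or the highest.

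At stake is the reading of the QTc, PR and QRS tables in a first-in-human trial that lists cardiac toxicity as an adverse event of clinical interest (SAP Table 5-1). Two programmers following SAP 5.5 could produce materially different Part C tables, and a reader of the dose cohorts could take longer follow-up for a drug effect.

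**Working it through.** The documents give no figure for this summary, so there is nothing to reproduce. The check has two steps: a count from the schedules, then a calculation of what the maximum does with no drug effect.

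**Step 1. Scheduled post-baseline recordings, from the protocol footnotes.**

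- A/B, stopping before C1D26: C1D1 4 h + EoT = 2 recordings in 2 visits.
- A/B, two cycles: C1D1 4 h (1) + C1D26 (2) + C2D1 (1) + EoT (1) = 5 recordings in 4 visits.
- A/B, six cycles: the same 5, plus C3D1 and C5D1 = 7 recordings in 6 visits.
- Part C, any duration: C1D1 4 h and EoT = 2 visits × 3 tracings = 6 tracings.

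**Step 2. Mean highest change from baseline with no drug effect.** Let b be the between-visit SD and w the SD between replicate tracings at a visit. The documents give neither, so I assume the range b/w = 5/5 to 12/10 ms, with 8/8 ms as a middle case. Errors are normal, and recordings at the same visit share the visit error. The baseline error has mean zero, so it drops out of the mean.

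For two independent values with SD s, the expected maximum is s/√π. This gives two rows exactly:

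- A/B, 2 recordings: √((b² + w²)/π). At 5/5: √(50/π) = 4.0. At 8/8: √(128/π) = 6.4. At 12/10: √(244/π) = 8.8 ms.
- Part C, triplicates averaged: √((b² + w²/3)/π). At 5/5: √(33.3/π) = 3.3. At 8/8: √(85.3/π) = 5.2. At 12/10: √(177.3/π) = 7.5 ms.

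The other rows were simulated with one million patients each; the simulation standard error is at most 0.02 ms.

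| Mean highest change, ms | 5/5 | 8/8 | 12/10 |
|---|---|---|---|
| A/B, 2 recordings | 4.0 | 6.4 | 8.8 |
| A/B, two cycles (5 recordings) | 8.0 | 12.7 | 17.5 |
| A/B, six cycles (7 recordings) | 9.4 | 15.1 | 20.7 |
| Part C, literal rule (highest of 6 tracings) | 7.8 | 12.4 | 16.4 |
| Part C, triplicates averaged | 3.3 | 5.2 | 7.5 |

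**Reading the table.**

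- Within A/B, the no-effect maximum at 8/8 ms goes from 6.4 to 12.7 to 15.1 ms as treatment lengthens. The ordering is the same at every SD pair.
- Within Part C, the choice of triplicate rule changes the result by a factor of 2.2 to 2.4 (16.4/7.5 to 7.8/3.3).
- Part C against a two-cycle A/B patient at 8/8 ms: 12.4 against 12.7 ms on the literal rule, but 5.2 against 12.7 ms if averaged.

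Mean highest change stands in here for the planned shift tables. I give no share above a cut-off, because SAP 5.5 names no interval cut-offs and such shares move strongly with the assumed SDs.

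**The case against.** A reader might infer that Part C will look free of QTc prolongation next to KPT-9274 alone because it is measured less often. The documents do not support that. The inference needs the triplicates to be averaged, and the SAP contains no such rule. On its literal wording, Part C and a two-cycle A/B patient come out almost equal. A six-cycle A/B patient is still higher, and an A/B patient who stops before C1D26 is lower.

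A reader might also infer that Part C is pooled with Parts A/B, because SAP 5 has "outputs presented by part and cohort and for all patients combined". The same sentence begins by separating tumour types. Part C is melanoma only, so the combined column need not merge it with the mixed A/B population. Protocol 9.1 presents safety separately for Part A, Part B and the two Part C dose levels. No between-part ECG comparison is planned, and safety analyses are descriptive and untested, so no error rate is involved. Part C also differs in tumour type, partner drug and eligibility, so such a comparison would be confounded anyway.

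By-visit summaries are not wholly missing. SAP 2.1 calls for statistics at each scheduled time point where applicable. Protocol 9.8.3 plans change from baseline at each evaluation under a heading that also covers 12-lead ECG, and SAP 1.7 declares no departure from the protocol's statistical section. Nor does the schedule slip change what is collected, since SAP 1.5 refers to the protocol for the schedule. Finally, worst-value tables that depend on time observed are common in safety reporting.

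All of this limits the harm. It does not correct the schedule, supply a triplicate rule, or put a by-time-point ECG table into SAP 5.5, which is where a programmer will look.

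**Conclusion.** The point holds in a limited form. Three things follow from the documents alone: SAP 5.5 gives the wrong schedule for Part C, the Part C analysis value is undefined, and the A/B maximum is taken over a count that rises with time on drug (2, 5 and 7 scheduled recordings in the examples).

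The millisecond sizes rest on assumed SDs, normal errors, no drug effect and no unscheduled ECGs. Over that SD range, going from two to six cycles raises the no-effect maximum from 8.0–17.5 to 9.4–20.7 ms. Leaving the Part C triplicates unaveraged gives 7.8–16.4 rather than 3.3–7.5 ms. The size of any difference between Part C and A/B cannot be stated until the triplicate rule is fixed. No planned inference is affected; what is at risk is how the descriptive tables are read.

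**What to change.** In SAP 5.5:

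1. Give the Part C schedule as the protocol has it, separately from Parts A/B.
2. State that Part C triplicates are averaged at each time point, for both baseline and post-baseline values.
3. Add actual value and change from baseline by scheduled time point for PR, QRS and QTc, as SAP 5.4 does for vital signs and in line with protocol 9.8.3. Identify C1D1 4 h and EoT as the post-baseline time points common to all parts. Even there, single and averaged triplicate values differ in precision: at 8/8 ms the two-value maximum is 6.4 ms for A/B and 5.2 ms for Part C.
4. Keep the highest-value shift tables as an outlier display by part, with a footnote giving the number of ECGs per patient.

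The cost is SAP wording and one table from data already scheduled for collection. No extra ECGs are needed.
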